#### **Secondary objectives**

In secondary analyses, all analyses above will be performed in the following *a priori* specified subgroups: 1) myocarditis case definition (based on criteria outlined in Section 9.2.1 – Inclusion Criteria); 2) age group at index date, to be determined based on the distribution of cases (e.g. less than 40 years of age versus 40+ years; <18 years versus 18-39 years versus 40+ years); 3) sex; and 4) available follow-up time (years).

In additional secondary analyses, we will assess the PPV of myocarditis diagnosis definitions that were created using algorithms in the EHR compared with those cases that are validated based on the review of the electronic medical notes as specified in Section 9.6.

Detailed methodology for summary and statistical analyses of data collected in this study will be documented in an SAP, which will be dated, filed and maintained by the sponsor. The SAP may modify the plans outlined in the protocol; any major modifications of primary endpoint definitions or their analyses would be reflected in a protocol amendment.

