#### **Secondary objectives:**

- 1. To examine the risk factors in each myocarditis cohort stratified by age group at diagnosis, sex, time period and follow-up time (years).
- 2. To assess and compare the validity of myocarditis diagnosis case definitions in administrative data for each cohort, via calculating the PPV using electronic medical record review.

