### 9.5. Study size

This is a NI study with no *a priori* hypotheses specified; therefore, sample size calculations are not applicable. Based on initial feasibility assessment of the Optum EHR database, there were approximately 240 myocarditis cases within 21 days of mRNA vaccination, 1,730 myocarditis cases after SARS-CoV-2 infection, and 7,200 myocarditis cases prior to 01 November 2019. In addition, the large size of the database will allow for matching of each myocarditis case with controls for the risk factor analyses.

 CFR 164.514(b)(1).

<sup>[2] Guidance Regarding Methods for De-identification of Protected Health Information in Accordance with the Health Information Insurance Portability and Accountability Act (HIPAA) Privacy Rule (Dated as September 4, 2012, as first released on November 26, 2012).

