## 9.7. Data analysis

# **Primary objective**

In primary analyses, descriptive statistics will be presented to characterize myocarditis patients in terms of demographic and clinical characteristics (including clinical characteristics of the myocarditis episode, as well as clinical history of the patient) as of the index date (date of myocarditis diagnosis code for myocarditis cases, or matched month/year among the control group). Specific demographics and clinical characteristics of interest are described in Section 9.3. Descriptive statistics will include counts and percentages for categorical data. For continuous variables, we will provide statistics such as mean, median, standard deviation, and range.

Additionally, appropriate statistical models such as conditional logistic regression or generalized estimating equations (GEE) incorporating non-independence of observations will be described in greater detail in the SAP. These models will estimate odds ratios (ORs) and 95% CIs of associations between demographics, clinical characteristics, and empirical model identified risk factors (based on either a stepwise selection approaches or via statistical significance in univariate models) and myocarditis. Models may incorporate laboratory based prognostic indices, severity status, clinical risk factors noted in Section 9.3 along with potential empirical model identified risk factors. These models will be run for the myocarditis cases and controls identified with ICD-10-CM codes in the EHR, and according to the inclusion and exclusion criteria as provided in Section 9.2, as well as for the cases that are validated by clinician reviews as myocarditis using the available Brighton Collaboration Criteria and information in medical record notes, as specified in Section 9.6. Model parameters will be detailed in the SAP.

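### Subgroup analyses re-run factor selection inside each age, sex and follow-up stratum, so in Cohort 1 a uniform risk factor may look subgroup-specific by chance; the age groups are called a priori but are still open

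*Protocol*

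**What the plan says.** Section 9.7, under the secondary objectives, states: "In secondary analyses, all analyses above will be performed in the following" subgroups, which it describes as *a priori* specified. They are case definition, age, sex and follow-up time. The age item reads "age group at index date, to be determined based on the distribution of cases (e.g. less than 40 years of age versus 40+ years", followed by a second example with three groups (under 18, 18 to 39, 40 and over). The abstract (Section 4) repeats both the label and the open age item.

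The analyses being repeated are those of the primary objective in Section 9.7. They include models with risk factors identified empirically, "based on either a stepwise selection approaches or via statistical significance in univariate models". On output the section says: "These models will estimate odds ratios (ORs) and 95% CIs of associations".

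The purpose comes from secondary objective 1 in Section 8: "To examine the risk factors in each myocarditis cohort stratified by age group at diagnosis, sex, time period and follow-up time (years". Section 9.5 gives the smallest cohort as "approximately 240 myocarditis cases within 21 days of mRNA vaccination"; Cohorts 2 and 3 have about 1,730 and 7,200 cases. Model details are left to the SAP.

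**The concern.** There are two linked problems.

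**Selection inside strata.** Read as written, repeating all analyses means that factor selection is run again within each stratum. Whether a factor is selected depends on stratum size as well as on the association. A factor that acts equally in men and women can pass in the larger stratum and fail in the smaller one. An empirically chosen factor may then have a reported odds ratio in one stratum and none in the other, so the estimates cannot be compared. What remains is a contrast between selected here and not selected there, which is not evidence of a difference.

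**The label.** A grouping still to be set from the data is not *a priori* specified. Nothing requires the same age groups in all three cohorts, although the primary objective is to compare factors across them.

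The post-vaccination cohort has most at stake. It is the smallest, and Section 7 says the study may help to put safety events in context and to inform eligibility criteria of future trials. An age- or sex-specific vaccine risk factor that arose from stratum size would be an unfortunate input to either.

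**Working it through.** The plan gives no power, threshold or subgroup error rate to reproduce; Section 9.5 says sample size calculations do not apply. What follows is illustrative.

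**Inputs from the protocol.** Cases: 240, 1,730 and 7,200 (Section 9.5). Sex: the female-to-male ratio of 1:1.5 to 1:1.7 in Section 7 gives 1.5/2.5 = 60% to 1.7/2.7 = 63% male, and 62% is used. That ratio comes from pre-COVID series, so applying it to Cohorts 1 and 2 is an assumption.

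**Assumed.** Factor prevalence in controls p0 of 5%, 10% or 20%; 4 controls per case; matching ignored; the same true odds ratio (1.5 or 2.0) in both sexes; selection at two-sided 5%, as 95% intervals imply; one factor at a time.

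**Step 1: strata in Cohort 1.** 0.62 × 240 = 148.8 male and 91.2 female cases.

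**Step 2: chance of significance in one stratum.** With prevalence in cases p1 = OR·p0 / (1 − p0 + OR·p0), power = Φ[(p1 − p0 − 1.96·SE0)/SE1]. SE0 is the pooled and SE1 the unpooled standard error of the difference. For p0 = 10% and OR = 1.5, p1 = 0.1429:

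- Men: SE0 = 0.0285, SE1 = 0.0312; power = Φ(−0.417) = 0.338.
- Women: SE0 = 0.0364, SE1 = 0.0399; power = Φ(−0.716) = 0.237.

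**Step 3: significant in one sex only.** P = a(1 − b) + b(1 − a) = 0.338 × 0.763 + 0.237 × 0.662 = 0.415.

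| Prevalence | OR | Power, men | Power, women | One sex only |
|---|---|---|---|---|
| 5% | 1.5 | 0.223 | 0.163 | 31.3% |
| 5% | 2.0 | 0.545 | 0.394 | 51.0% |
| 10% | 1.5 | 0.338 | 0.237 | 41.5% |
| 10% | 2.0 | 0.762 | 0.575 | 46.0% |
| 20% | 1.5 | 0.490 | 0.337 | 49.7% |
| 20% | 2.0 | 0.917 | 0.756 | 28.6% |

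Simulating the same set-up moves the ends by about a point at most, hence the quoted 28% to 52%.

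**Step 4: other cohorts, same formula.** Cohort 2 runs from 41.4% (5% prevalence, OR 1.5) through 15.8% (10%, OR 1.5) to 2.1% or less at OR 2.0. Cohort 3 never exceeds 0.6%.

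**Step 5: age groups** (assumed case mixes, 10% prevalence, simulation of significance in some but not all groups). At OR 1.5, Cohort 1 gives 53% with three groups (20/40/40) and 42% with two (60/40). Cohort 2 gives 50% with three groups and about 14% with two; at OR 2.0 with three groups it gives about 2%. Cohort 3 stays below 1%.

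**Step 6: comparison with an interaction test.** In the same simulations, a 5% test of whether the odds ratios differ between strata is wrongly positive in about 4% to 5% of studies.

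**Step 7: precision of that estimate in Cohort 1.** For p0 = 10% and OR = 1.5, the variance of the log odds ratio is 1/21.3 + 1/127.5 + 1/59.5 + 1/535.7 = 0.0735 in men and 0.0735 × 148.8/91.2 = 0.120 in women. The standard error of the log ratio of odds ratios is √0.1935 = 0.44, so its 95% interval spans a factor of exp(1.96 × 0.44) = 2.4 each way.

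**The case against.** **The SAP may settle it.** An interaction test, an exploratory label and model details commonly belong in the SAP, and the protocol defers to it. A reader might infer that no test of subgroup difference is planned; the protocol alone cannot show that. This stands, and the point does not rest on it. It rests on what Section 9.7 does state: selection repeated per subgroup, and an *a priori* label on groups not yet chosen.

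**Stratum-specific estimates answer the objective.** Secondary objective 1 asks for risk factors within strata, and intervals can be compared by eye. This is fair for factors reported in every stratum. It fails for those whose presence depends on selection in that stratum.

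**The study has an exploratory frame.** It declares no prior hypotheses and a partly hypothesis-generating purpose. That softens the consequences, but sits poorly with calling the subgroups *a priori*.

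**Data-driven age groups.** A reader might infer that taking cuts from the case distribution inflates false positives. Choosing groups for adequate counts, without looking at associations, does not by itself do so. The two examples also share the cut at 40, so the freedom is narrow. The fault is that the choice stays open under a label saying it is closed.

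**Larger headline figures.** One could count any significant stratum for a null factor over all strata and cohorts and reach about 56% under similar assumptions. That is not a rate of false subgroup differences. Interaction tests also accumulate: three independent ones per cohort give 1 − 0.95³ = 14.3%.

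**Conclusion.** The concern holds as a fault in the stated method and wording of Section 9.7 and the abstract, mainly for Cohort 1. There, a factor acting equally in both sexes may be significant in one sex only in about 28% to 52% of studies, against about 4% to 5% for an interaction test. In Cohort 2 the sex figure runs from near 0 to about 41%, depending on prevalence and odds ratio. In Cohort 3 it is under 1%. Prevalence, control ratio, age mix, threshold and the use of the pre-COVID sex ratio are assumptions, and full stepwise selection with matching would change the exact values.

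The documents do not support saying that chance differences will be reported as subgroup-specific factors, or that all cohorts are affected alike. The *a priori* inconsistency needs no assumption. The change is worth making, but the whole-cohort analyses are not affected by this point.

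**What to change.** In Section 9.7, and in the matching abstract text:

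1. Select factors once per cohort, in the main model, and hold that list fixed across subgroups. Report stratum-specific odds ratios with 95% intervals for every factor on it. Judge subgroup differences by factor-by-subgroup interaction estimates (ratio of odds ratios with 95% interval), not by selection or significance in one stratum.
2. Name one age grouping for all three cohorts, for example one of the protocol's own two, with a rule based on case counts, stated beforehand, for collapsing groups. Otherwise drop the *a priori* label.

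This costs wording plus interaction terms in models already planned, and needs no new data. The downside is fewer subgroup-specific claims. Interaction estimates in Cohort 1 will also be imprecise, with an interval of roughly a factor of 2.4 each way for sex in the worked case.

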# 9.8. Quality control

All codes and/or code algorithms will be reviewed by the Safety Risk Lead in the Safety Surveillance and Risk Management group for the Pfizer COVID-19 vaccine program, as well as the protocol authors. The ICD-9-CM and ICD-10-CM codes used in the study will be reviewed against relevant codes used in the Food and Drug Administration (FDA) Sentinel program whenever applicable; if there are any discrepancies, the Sentinel codes will be used unless there is a strong rationale to use internally developed ICD codes and/or ICD algorithms instead. Additional validation of the code lists will be performed if warranted. All efforts will be made to ensure quality and safe storing of data and reports. Quality control (QC) checks will be performed on all SAS programming, data tables, and reports generated in the course of this research. QC findings and documentation of remedial action will be maintained. Storage of programming, data, and reports will be carried out per standard procedures, and as specified in Section 9.6.

In the validation study, after the Optum NLP team creates key term tags for use in the snippet review for the two Optum clinicians who will review patient notes with these key terms mentioned, the two clinicians will record their findings from the notes regarding whether the notes support a myocarditis diagnosis based on the Brighton Criteria. These results will be provided to the HEOR team for review and any clarifications or questions will be managed between the two groups until resolved.

#### 9.9. Limitations of the research methods

This study has several strengths. First, it is a population-based study in a real-world population, increasing generalizability and external validity. Second, the Optum EHR database has both inpatient and outpatient data, in addition to laboratory data and microbiology results for a subset of patients that could be leveraged. In addition, the large sample size will enable the capture of a range of pre-specified health outcomes and clinical conditions, while the longitudinal nature of the data will allow us the ability to track risk factors, clinical manifestations, and changes in prognostic laboratory values over time.

However, the study also has several limitations. As is the case in any study based on secondary data sources, outcome misclassification is a possibility, as delayed and misdiagnosis of myocarditis is potentially high. However, the validation sub-study, which is being conducted concurrently, will allow us to evaluate potential misclassification of myocarditis, as well as key risk factors of interest. Diagnostic codes may also be incorrect or may be included as part of the diagnostic rule-out process or a record of a historical myocarditis event rather than an indication of a recent myocarditis, however by incorporating a multi-tier treatment and diagnostic algorithm to identify myocarditis, it will allow us to evaluate the robustness and accuracy of cases identified based on diagnosed criteria alone versus criteria that requires additional data such as medication or procedures for verification of

myocarditis. Laboratory results and vital signs/other biometric measures may be incomplete and therefore only available for a subset of the patients. Another limitation inherent to EHR databases is that information on prescriptions recorded for outpatients in this database does not necessarily indicate that the medication was consumed or taken as prescribed; similarly, medications filled over the counter or provided as samples by the physician may not be recorded in the database. Vaccine administrations or SARS-CoV-2 infections may not be recorded in the EHR, and so myocarditis after vaccination or COVID-19 infection may be missed. Similarly, due to the nature of EHR data, conditions not requiring treatment or office visits tend to be systematically under-recorded; therefore, it is possible that this study may only capture severe conditions that are considered in the risk factor models. Patients may have received health care outside of the network of providers and healthcare organizations that contribute to the Optum databases, or prior to having the index diagnosis and we may not be able to exclude the possibility that a patient was diagnosed with myocarditis, as well as other risk factors, prior to entry into a healthcare system where Optum has EHR access. Furthermore, if observed results using ICD-9 codes significantly differ from observed results using ICD-10 codes as a result of Centers for Medicare & Medicaid Services (CMS) and the National Center for Health Statistics (NCHS) ICD-9 to ICD-10 transition, we may modify our definitions as necessary.

### 9.10. Other aspects

Not applicable.

#### 10. PROTECTION OF HUMAN SUBJECTS

#### 10.1. Patient information

All parties will comply with all applicable laws, including laws regarding the implementation of organizational and technical measures to ensure protection of patient personal data. Such measures will include omitting patient names or other directly identifiable data in any reports, publications, or other disclosures, except where required by applicable laws.

Patient personal data will be stored at Optum in encrypted electronic and will be password protected to ensure that only authorized study staff have access. Optum has implemented appropriate technical and organizational measures to ensure that the personal data can be recovered in the event of disaster. In the event of a potential personal data breach, Optum shall be responsible for determining whether a personal data breach has in fact occurred and, if so, providing breach notifications as required by law.

#### 10.2. Patient consent

As this study does not involve data subject to privacy laws according to applicable legal requirements, obtaining informed consent from patients by Pfizer is not required.

### 10.3. Institutional review board (IRB)/Independent ethics committee (IEC)

IEC/IRB review was not required for this secondary data analysis study.

# 10.4. Ethical conduct of the study

The study will be conducted in accordance with legal and regulatory requirements, as well as with scientific purpose, value and rigor and follow generally accepted research practices described in Guidelines for Good Pharmacoepidemiology Practices (GPP) , European Medicines Agency (EMA) European Network of Centres for Pharmacoepidemiology and Pharmacovigilance (ENCePP) Guide on Methodological Standards in Pharmacoepidemiology , FDA Guidance for Industry and FDA Staff: Best Practices for Conducting and Reporting Pharmacoepidemiologic Safety Studies Using Electronic Healthcare Data , and Good practices for real-world data studies of treatment and/or comparative effectiveness: Recommendations from the joint ISPOR-ISPE Special Task Force on real-world evidence in health care decision making .

#### 11. MANAGEMENT AND REPORTING OF ADVERSE EVENTS/ADVERSE REACTIONS

# 11.1. Structured Data Analysis

This study involves data that exist as structured data by the time of study start. In these data sources, it is not possible to link (i.e., identify a potential association between) a particular product and medical event for any individual. Thus, the minimum criteria for reporting an AE (i.e., identifiable patient, identifiable reporter, a suspect product, and event) cannot be met.

### 11.2. Unstructured Data Analysis

This study protocol requires human review of patient-level unstructured data; unstructured data refer to verbatim medical data, including text-based descriptions such as medical records, images of physician notes, neurological scans, x-rays, or narrative fields in a database. The reviewer is obligated to report AEs with explicit attribution to any Pfizer drug that appear in the reviewed information (defined per the patient population and study period specified in the protocol). Explicit attribution is not inferred by a temporal relationship between drug administration and an AE but must be based on a definite statement of causality by a healthcare provider linking drug administration to the AE.

The requirements for reporting safety events on the non-interventional study (NIS) adverse event monitoring (AEM) Report Form to Pfizer Safety are as follows:

- All serious and non-serious AEs with explicit attribution to any Pfizer drug that appear in the
  reviewed information must be recorded on the data collection tool (e.g., chart abstraction form)
  and reported, within 24 hours of awareness, to Pfizer Safety using the NIS AEM Report Form.
- Scenarios involving drug exposure, including exposure during pregnancy, exposure during breast
  feeding, medication error, overdose, misuse, extravasation, lack of efficacy, and occupational
  exposure associated with the use of a Pfizer product must be reported, within 24 hours of
  awareness, to Pfizer Safety using the NIS AEM Report Form.
- For exposure during pregnancy in studies of pregnant women, data on the exposure to "PF-07302048 during pregnancy, are not reportable unless associated with serious or non-serious AEs.

 For these AEs with an explicit attribution or scenarios involving exposure to a Pfizer product, the safety information identified in the unstructured data reviewed is captured in the Event Narrative section of the report form, and constitutes all clinical information known regarding these AEs.
 No follow-up on related AEs will be conducted.

All the demographic fields on the NIS AEM Report Form may not necessarily be completed, as the form designates, since not all elements will be available due to privacy concerns with the use of secondary data sources. While not all demographic fields will be completed, at the very least, at least one patient identifier (e.g., gender, age as captured in the narrative field of the form) will be reported on the NIS AEM Report Form, thus allowing the report to be considered a valid one in accordance with pharmacovigilance legislation. All identifiers will be limited to generalities, such as the statement "A 35-year-old female..." or "An elderly male..." Other identifiers will have been removed.

Additionally, the onset/start dates and stop dates for "Illness," "Study Drug," and "Drug Name" may be documented in month/year (mmm/yyyy) format rather than identifying the actual date of occurrence within the month /year of occurrence in the day/month/year (DD/MMM/YYYY) format.

All research staff members must complete the following Pfizer training requirements:

• "Your Reporting Responsibilities (YRR) with Supplemental Topics."

These trainings must be completed by research staff members prior to the start of data collection. All trainings include a "Confirmation of Training Statement" (for signature by the trainee) as a record of completion of the training, which must be kept in a retrievable format. Copies of all signed training statements must be provided to Pfizer.

